14. RETENTION OF RECORDS

U.S. FDA regulations (21 CFR §312.62[c]) and the ICH Guideline for GCP (see Section 4.9 of the guideline) require that records and documents pertaining to the conduct of clinical trials and the distribution of investigational drug, patient records, consent forms, laboratory test results, and medication inventory records must be retained for 2 years after the last marketing application approval in an ICH region or after at least 2 years have elapsed since formal discontinuation of clinical development of the investigational product. All state and local laws for retention of records also apply.

Appendices

Appendix A: INHIBITORS AND INDUCERS OF CYP3A

NOTE: Itraconazole and ketoconazole can be replaced with voriconazole for study subjects.

Inhibitors of CYP3A	Inducers of CYP3A
Strong inhibitors:	
indinavir	carbamaze
nefnavir	nevirapine
ritonavir	barbiturates
clarithromycin	glucocorticoids
Itraconazole	modafinil
Ketoconazole	oxcarbazepine
nefazodone	pioglitazone
saquinavir	troglitazone
suboxone	pioglitazone
telithromycin	Strong CYP3A inducers
cobicistat	avasimibe
boceprevir	carbamazepine
mibefradil	phenobarbital
telaprevir	phenytoin
troleandomycin	rifabutine
posaconazole	rifampin
voriconazole	St. John's Wort
Moderate inhibitors:	
aprepitant	
amprenavir	
amiodarone	
atazanavir	
ciprofloxacin	
isavuconazole	
crizotinib	
darunavir	
dronedarone	
erythromycin	
diltiazem	
fluconazole	
fosamprenavir	
grapefruit juice	
Seville orange juice	
verapamil	
imatinib	
Weak inhibitors:	
cimetidine	
fluvoxamine	
All other inhibitors:	
chloramphenicol	
delavirdine	
gestodene	
mifepristone	
norfloxacin	
star fruit	

Appendix B: Preparation Worksheet for NG or OG Tube Administration of Ibrutinib**PREPARATION WORKSHEET FOR IBRUTINIB**Preparation Worksheet for Ibrutinib for each dose that is prepared.**IP Preparation Steps for Ibrutinib 140 mg****Preparation Date:** dd/ mmm/ yyyy**Subject No.** _____ HH: mm**Preparation area:****PREPARATION OF THE DRUG PRODUCT**

INSTRUCTIONS	RECORD	
1. Confirm the preparation area is clean and cleaning is performed according to site procedure.	  /   Performed by _____ Date _____	
2. Ensure the dispensing labels are prepared		
3. Remove 3 capsules from the bottle.	Medication Kit Number: _____	
4. Record the time the capsules are removed from the bottle.	dd / mmm / yyyy HH: mm	
5. Open the 3 capsules and place their contents into a glass beaker. Tap the capsule bodies and caps against the side of the beaker to remove any excess material remaining within the capsule bodies and caps.		
6. Prepare a glass beaker filled with 30 mL of water, add to the beaker with the capsule contents, and swirl/mix until the contents are uniform.	Volume of water in beaker (mL): _____	
7. Allow the dispersion to stand for at least 15 minutes.	Standing Start: HH: mm	
8. Affix an 18 gauge needle to a 60 mL syringe, briefly swirl the beaker, and draw the dispersed capsule contents into the syringe.	Standing End: HH: mm	

Ibrutinib for COVID 19

9. Prepare a glass beaker filled with 10 mL of water, add to the empty container to rinse, and draw up into the same syringe.	Volume of water in beaker (mL): _____	
10. Prepare a glass beaker filled with 10 mL of water, add to the empty container to rinse a second time, and draw up into the same syringe, leaving air between solution and plunger.	Volume of water in beaker (mL): _____	
11. Invert the syringe several times to ensure capsule material remains suspended and does not stick to the sides of the syringe.		
12. Draw the plunger back slightly to evacuate the tip. Close the syringe with a tip cap.		
13. Shake the syringe vigorously for approximately 1 min and allowed to stand for at least 30 minutes to allow for complete dispersion prior to dose administration.	Standing Start: ____ HH: ____ mm	Standing End: ____ HH: ____ mm
14. Fill in the variable text fields of the previously prepared dispensing labels and affix the label on the barrel of the syringe.		
15. Calculate expiry: Expiry time is 4 hours after the capsules are removed from the bottle.	Expiry date: dd / mmm / yyyy HH: mm	
16. Place the syringe in a tray or a suitable container in a horizontal position.		
Attestation of Dose Preparation steps 1-16	____ / ____ Performed by _____ Date	____ / ____ Checked by _____ Date
The prepared syringe is ready to be provided to the dose Administrator		

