7.3. Concomitant Medication Use Guidelines For Study Participants

Warfarin is excluded throughout the trial as is grapefruits and grapefruit juice, starfruit, and Seville oranges. Cancer therapy is also prohibited during the study. Medications allowed with caution are found in Appendices

A. All concomitant medications need to be documented in the electronic medical record.

Standard of Care COVID 19 Therapy

All standard of care therapy for COVID 19 that is not specifically prohibited in the protocol is acceptable and encouraged. Current standards of care can be found in Table 2 of Appendix C. It is acknowledged that standards of care are likely to change during the course of the study. Standard of care therapy should be considered in the context of toxicities expected with ibrutinib, and therapies that are expected to have overlapping toxicities should be used with caution.

Anticoagulants and Anti-platelet agents

Laboratory studies have shown that *in vitro* ibrutinib can prevent platelets from aggregating normally. While serious bleeding has been uncommon in patients treated to date, it is possible that treatment with the study drug could increase the risk of bruising or bleeding, particularly in subjects receiving oral anticoagulants or antiplatelet agents. Besides warfarin, which is prohibited, patients on the study may receive any other anticoagulants or antiplatelet agents at prophylactic or therapeutic doses. Subjects receiving anticoagulants and/or antiplatelet agents in conjunction with ibrutinib should be observed closely for any signs of bleeding or bruising and ibrutinib should be withheld in the event of any significant

bleeding events. Patients receiving both therapeutic anticoagulation and anti-platelet agents should be considered at higher risk for bleeding.

Inhibitors or inducers of CYP3A

As ibrutinib is primarily metabolized by CYP3A. Concomitant use of ibrutinib and drugs that strongly or moderately inhibit CYP3A can increase ibrutinib exposure, these should be avoided as possible. Avoid grapefruit and Seville oranges during ibrutinib treatment as these contain moderate inhibitors of CYP3A. Strong inhibitors of ibrutinib should be avoided during the course of the trial. Dose adjustment of ibrutinib due to concomitant use of CYP3A inhibitors should follow Table 1 below as applicable. See Appendices

A for a summary of cautionary medications.

Table 1: Ibrutinib Dose Modification Guidance for Co-Administration with CYP3A Inhibitors

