
Ibrutinib for COVID 19

Co-administered Drug	Recommended Ibrutinib Dose for the Duration of the Inhibitor Use ^a	Recommended Ibrutinib Dose for the Duration of the Study IF THE STARTING STUDY DOSE IS 280 mg
Mild CYP3A inhibitors	420 mg once daily. No dose adjustment required.	280 mg daily. No dose adjustment required
Moderate CYP3A inhibitors	280 mg once daily.	140 mg once daily
Voriconazole 200 mg twice daily Posaconazole suspension 100mg once daily, 100 mg twice daily, or 200 mg twice daily	140 mg once daily.	70 mg once daily
Posaconazole at higher doses ^b	70 mg once daily.	Discontinue ibrutinib
Other strong CYP3A inhibitors	Avoid concomitant use and consider alternative with less CYP3A inhibitory potential. If these inhibitors will be used short-term (such as anti-infectives for seven days or less), interrupt ibrutinib. If the benefit outweighs the risk and long-term dosing is required (more than seven days), reduce ibrutinib dose to 140 mg once daily for the duration of the inhibitor use.	Avoid concomitant use and consider alternative with less CYP3A inhibitory potential. If these inhibitors will be used short-term (such as anti-infectives for seven days or less), interrupt ibrutinib. If the benefit outweighs the risk and long-term dosing is required (more than seven days), reduce ibrutinib dose to 140 mg once daily for the duration of the inhibitor use.

a. Monitor for adverse reactions to ibrutinib (IMBRUVICA) and interrupt or modify dose as recommended (see Dosage and Administration).

b. Posaconazole at higher doses (posaconazole suspension 200 mg three times daily or 400 mg twice daily, posaconazole IV injection 300 mg once daily, posaconazole delayed-release tablets 300 mg once daily).

A list of common CYP3A inhibitors and inducers is provided in **Appendix A**. For further information, please refer to the current version of the ibrutinib IB and examples of inhibitors, inducers, and substrates can be found at <http://medicine.iupui.edu/clinpharm/ddis/main-table/>.

Tocilizumab has the potential to reduce ibrutinib concentrations, and thus should be used with caution

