8.1. Guidelines for Dose Suspension or Modification Due to Adverse Events

Adverse events (AEs) will be assessed and graded according to the National Cancer Institute Common Terminology Criteria for Adverse Events (CTCAE) version 5.0. Laboratory toxicities will be formally evaluated on days 8, 15, 22, and 29, unless determined to be clinically irrelevant by the principal investigator. These labs will be done \pm 3 days.

Treatment with study drug should be interrupted for any grade 3 or higher non-hematologic toxicity with at least possible association to ibrutinib, with the exception of electrolyte abnormalities, nausea, vomiting, or diarrhea, alopecia, or hypertension that can be managed with supportive medications.

Treatment with study drug should be interrupted for any grade 4 hematologic toxicity (or increase in grade by 2 levels if baseline toxicity exists) with at least possible association to ibrutinib with the exception of neutropenia that can be managed with growth factors, anemia/thrombocytopenia responsive to transfusion, or lymphocytosis/lymphocytopenia.

Once the toxicity has resolved to grade 1 or baseline, study drug can be restarted at the original dose. If toxicity recurs, the dose should be held and then decreased by one dose level as outlined in Table 2.

If drug needs to be held > 14 days and still considered possibly drug-related, study drug should not be restarted.

Table 2: Dose De-Escalation Schedule for Toxicity

Dose De-Escalation Schedule for Toxicity	
Dose Level	Study drug
Level 1 – Starting Dose	420 mg/day (Days 1-14)
Level 2	280 mg/day
Level 3	140 mg/day
Level 4	Discontinue

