8.2. Dose modification of study drug (Ibrutinib or placebo) for Hepatic Impairment

Patients who develop grade 2 increase in bilirubin or ALT/AST should have study drug dose reduced to 2 capsules (equivalent to 280 mg daily) for either arms. If liver function tests return to grade 1 levels, study drug can be increased to 3 capsules (equivalent to 420 mg daily). Patients who develop grade 3 or higher increase in bilirubin or AST/ALT or who have evidence of hepatic failure should have study drug discontinued permanently.

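### The tube-dosing worksheet (Appendix B) fixes every dose at three capsules (420 mg) and cannot record the reduced doses ordered in 8.2, Table 1 and Table 2

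*Combined protocol and SAP*

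**What the plan says.** Appendix B is headed as a "Worksheet for Ibrutinib for each dose that is prepared". Step 3 is "Remove 3 capsules from the bottle" and step 5 is "Open the 3 capsules and place their contents into a glass beaker". The entries to complete are kit number, times, water volumes and expiry. One person performs and another checks, under "Attestation of Dose Preparation steps 1-16". Section 10.1.1 describes one capsule strength, 140 mg.

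Lower doses are ordered elsewhere:

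- **8.2 (hepatic):** patients with a grade 2 rise in bilirubin or ALT/AST "should have study drug dose reduced to 2 capsules (equivalent to 280 mg daily) for either arms".
- **8.1 and Table 2 (toxicity):** "If toxicity recurs, the dose should be held and then decreased by one dose level as outlined in Table 2". The levels below 420 mg are 280 and 140 mg.
- **7.3 and Table 1 (CYP3A inhibitors):** "Dose adjustment of ibrutinib due to concomitant use of CYP3A inhibitors should follow Table 1 below as applicable". The 420 mg column goes to 280, 140 or 70 mg. For other strong inhibitors needed beyond seven days it says to "reduce ibrutinib dose to 140 mg once daily for the duration of the inhibitor use".

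Tube dosing is foreseen. Section 7.1.2 allows treatment to continue after respiratory failure, and inclusion criterion 7 admits patients who can take capsule content by tube.

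**The concern.** The worksheet is completed and signed dose by dose, so it is the document in hand when a tube dose is made. A reduced dose is prepared correctly only if staff depart from steps they then attest. No sentence in the protocol says whether the worksheet or the current dose order prevails.

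The patients exposed are those whose dose was lowered for safety. Section 10.1.3 counts any dose above the specified one as an overdose. For a patient on a CYP3A inhibitor the reduction is there because the inhibitor raises ibrutinib exposure, so a full dose would undo it.

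**Working it through.** **Worksheet dose.** Capsules in steps 3 and 5: 3. Strength (10.1.1): 140 mg. 3 × 140 = 420 mg, which is the full daily dose given in 10.1.2. The 140 mg in the worksheet title is the capsule strength and does not set the dose.

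**Instructions in force with a 420 mg start.**

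| Source | Doses ordered (mg) | Count |
|---|---|---|
| Table 1, 420 mg column | 420, 280, 140, 70, 140 | 5 |
| Table 2 | 420, 280, 140 | 3 |
| 8.2 | 280 | 1 |
| Total | | 9 |

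**Comparison with 420 mg.**

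| Ordered dose | Instructions | Capsules needed | Worksheet dose ÷ ordered dose |
|---|---|---|---|
| 420 mg | 2 | 3 | 1 |
| 280 mg | 1 + 1 + 1 = 3 | 280/140 = 2 | 420/280 = 1.5 |
| 140 mg | 2 + 1 = 3 | 140/140 = 1 | 420/140 = 3 |
| 70 mg | 1 | 70/140 = 0.5 | 420/70 = 6 |

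The instructions below the worksheet dose number 3 + 3 + 1 = 7 of 9. These are instructions, not patients. The documents give no number of tube-dosed patients and no rate of dose reduction.

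**The 70 mg dose.** It is half of the only capsule strength described. The worksheet has no step for giving part of the suspension. By mouth, 7.2 requires capsules to be swallowed whole, so that route cannot deliver 70 mg either. The gap belongs to Table 1 as much as to Appendix B.

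**Tube wording, side by side.**

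| Place | Preparation | Tube | Patients |
|---|---|---|---|
| Inclusion 7 | opened | nasogastric or enteral feeding | not limited to ventilated patients |
| 7.2 | crushed under water | nasogastric or orogastric | ventilated, cannot swallow |
| 10.1.2 | opened | nasogastric or orogastric | ventilated, cannot swallow |
| Appendix B | opened | nasogastric or orogastric | not stated |

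Inclusion 7 relies on 7.2, but the patients named in 7.2 are excluded at screening by the ventilation criterion in 5.2. Read strictly, 7.2 describes no route for someone tube-fed at entry. The intent is clear enough that this is mainly a matter of alignment.

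**The case against.** The best defence is that three capsules is simply the default. Sections 7.2 and 10.1.2 also state it for oral dosing, and nobody reads those as cancelling Section 8. Section 8.2 gives its reduction in capsules and for both arms. Tube doses are prepared in collaboration with the hospital pharmacy and checked by a second person. A careful pharmacist would probably follow the current order, and the dispensing label, whose content is not shown, may carry the dose. This makes an error less likely. It does not remove the conflict: 7.2 and 10.1.2 describe the usual regimen, whereas the worksheet is a record of each dose, and the second person checks the same three-capsule steps.

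Reductions will also be limited in a 14-day course. A first interrupting toxicity leads to a restart at the original dose, and only a recurrence lowers it. Grade 3 or higher hepatic toxicity ends study drug. Chronic strong CYP3A inhibitors are excluded, and strong inhibitors in the last Table 1 row used for seven days or less lead to interruption. All of this stands. However, 8.2 and the Table 1 rows for moderate inhibitors and voriconazole apply at once. Liver tests are done at least twice weekly on study drug, and Appendix A names voriconazole as a replacement for two other azoles.

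A reader might pool both Table 1 columns and conclude that 11 of 13 instructions are exceeded. The columns are mutually exclusive: the second applies only if the starting dose is 280 mg. In that case Table 2 and 10.1.2 would still state 420 mg as well, so that mismatch is not particular to the worksheet.

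**Conclusion.** The conflict is real and should be corrected. With a 420 mg start, the written tube procedure exceeds 7 of 9 dosing instructions, by 1.5, 3 or 6 times. This rests on reading the worksheet literally and on 140 mg being the only strength supplied. It is a safety and dose-delivery inconsistency, and its frequency is unknown and probably small.

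Three stronger inferences are not supported:

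- **A count of affected patients.** Any figure needs assumed rates of tube dosing and of dose reduction. The primary event also includes death, high-flow oxygen and noninvasive ventilation, which need not involve a tube, so event rates do not supply the number.
- **An effect on the interim safety rules.** With 15 patients per arm, one treatment-related grade 5 event against none is 1/15 = 6.7% and meets the 5% criterion whether or not a tube was used. Nothing ties that to the worksheet.
- **Automatic unblinding.** Under 10.1.3 unblinding follows only if signs of overdose meet a serious adverse event criterion. Only then does 8.3 end study drug.

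No effect on power, type I error or sample size is claimed.

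**What to change.** 1. In Appendix B steps 3 and 5, replace the fixed three with the number of capsules for the current ordered dose (3, 2 or 1).
2. Add entries for dose level and capsule count, and bring them under the two-person attestation. Use the same form and counts in both arms so that the blind is kept.
3. For 70 mg, state in both Table 1 and Appendix B either a partial-dose step specified by pharmacy or that study drug is held. This has to cover oral dosing too.
4. As minor alignment, change the crushing instruction in 7.2 to opening and dispersing per Appendix B. Word 7.2 and 10.1.2 for any patient unable to swallow capsules, consistent with inclusion 7.

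The cost is a revised worksheet, a few wording changes and one pharmacy decision on 70 mg. Sample size, visit schedule and analysis are unchanged.

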Appendix C: Institutional guidelines for management of COVID-19

Treatment Setting	Treatment Recommendations Regardless of Age, Comorbidities, or Immunocompromised Status
Outpatient Setting	Supportive Care
Inpatient Setting*	Mild Disease – Without pneumonia and requiring <4L of new O ₂ Supportive Care
	Moderate Disease – Pneumonia requiring hospitalization, not meeting criteria for severe disease OR no evidence of pneumonia, but requiring ≥4L of new O ₂ Consider Treatment**
	Severe Disease – Requiring mechanical ventilation OR impending respiratory failure requiring intubation (RR>30 breaths/min; O ₂ saturation ≤93% on room air; PaO ₂ /FiO ₂ ratio <300mmHg) Consider Treatment

*Treatment requires approval 24/7 – see [Appendix C](#)

**Strongly consider treatment if duration of illness ≥ 7 days

Table 1: Treatment Recommendations for Highly Suspected / Confirmed COVID-19

Setting / Severity of Illness	Description	Treatment
Outpatients	All outpatients	Supportive care
Inpatients Mild Disease	Inpatients without pneumonia and SpO ₂ > 94% on room air	
Inpatients Severe Disease	Inpatients with SpO ₂ ≤ 94% on room air; requiring supplemental oxygen, mechanical ventilation, or ECMO	Consider treatment and/or enrollment in clinical trial(s)
Treatment recommendations regardless of age, comorbidities, or immunocompromised status		

Table 2: Adjunctive Antimicrobial Therapies to Consider in Patient Meeting Criteria for Treatment

Medication	Dose	Indication for Use	Additional Information
Remdesivir	200 mg IV for 1 day Then 100 mg IV daily for 4 – 9 days (Refer to Table 5 in Appendix A) No adjustment for renal impairment/ ECMO	• Non-FDA-approved agent available via emergency use authorization	
 See Appendix A for additional information on how to obtain this product Baseline and daily serum creatinine and hepatic function labs required Avoid combination therapy with hydroxychloroquine/ chloroquine due to in vitro antagonism The clinical relevance of in vitro CYP drug-drug interactions has not been established.

Ibrutinib for COVID 19

Comorbidities: obesity, asthma, chronic heart, lung, kidney, or liver disease; poorly controlled diabetes mellitus; pregnancy; or active malignancy

Please refer to <https://osu.app.box.com/s/sgvwyweea5xx7mjoghfimcaekpq52hv> for most updated version of institutional COVID 19 guidelines

Table 2: Adjunctive Antimicrobial Therapies to Consider in Patient Meeting Criteria for Treatment			
Medication	Dose	Indication for Use	Additional Information
Remdesivir	
 200 mg IV x 1 day Then 100 mg IV daily x 4-9 days No adjustment for renal impairment/ ECMO 	
 Non-FDA-approved agent available via compassionate use, expanded access, and emergency use authorization 	
 See Appendix A for additional information on how to obtain this product Baseline and daily hepatic function labs required
Hydroxychloroquine (Plaquenil®) PO Suspension (intubated) or Tablets (not intubated)	
 400 mg BID x 1 day Then 200 mg PO BID x 4 days No adjustment for renal impairment If inadequate supply, may substitute chloroquine 500 mg PO x 5-10 days (Appendix B) May extend course up to 10 days based on clinical response 	
 Consider use in patients who do not meet criteria for remdesivir or while awaiting remdesivir 	
 May cause QTc prolongation (See Appendix B) Tablets cannot be crushed – use suspension for tube administration
Convalescent Plasma	
 Refer to Convalescent Plasma Expanded Access Program Workflow for information regarding eligibility, patient consent, and the approval process for COVID-19 patients in whom this therapy is recommended by an Infectious Disease provider 		
Non-Antimicrobial Medications	
 Additional recommendations for non-antimicrobial medications associated with complications and comorbidities linked to COVID-19 (e.g. IVIG, tocilizumab, corticosteroids, ACEI/ARBs, NSAIDS, etc.) refer to the Inpatient Evaluation and Management Guideline for COVID-19 		

*The appendix in the tables refer to an external document
